Statistical Methods	
Sample Size:
 
For the primary efficacy endpoint of proportion of subjects with at least one CSE, assuming a 20% true rate of at least one CSE, two-sided 5% Type 1 error and 80% power, the sample size to rule out a CSE rate less than or equal to 10% requires 86 evaluable subjects in the primary analysis group. The trial will have met the primary endpoint if at least 15/86 (17.4%) subjects have at least one CSE. The 95% two-sided Clopper-Pearson exact confidence bound at 17.4% is (10.1%, 27.1%).
 
Efficacy
 
A descriptive analysis of the baseline subject and tumor characteristics will be performed. Quantitative data will be presented as a standard set of summary statistics (n/mean (standard deviation)/median/minimum/maximum). Categorical data will be expressed as frequency (%).
 
For the primary endpoint analysis, the proportion of subjects undergoing NIR imaging with at least 1 CSE will be identified and tested under the following null hypothesis:
 
Ho: $P \leq 0.10$
 
The alternative hypothesis states that the proportion of subjects undergoing NIR imaging with at least 1 CSE will be greater than the chosen margin of 0.10:
 
Ha: $P > 0.10$
 
At 86 evaluable subjects, this trial is power at 80% to reject the null hypothesis of a 10% or fewer of subjects experiencing at least one CSE. Two-sided 95% exact confidence intervals for the proportion of subjects with at least one CSE will be constructed.
 
For the secondary endpoint analysis sensitivity, PPV, and 1-PPV will be calculated and presented along with 95% confidence intervals using GEE model analysis to factor in within-subject correlation for subjects with multiple tumors.
 
Safety:
 
Adverse event (AE) data will be listed by subject. Treatment-emergent adverse events (TEAEs), serious adverse events (SAEs), and AEs leading to study drug discontinuation will be summarized by system organ class and preferred term using the current version of the Medical Dictionary for Regulatory Activities (MedDRA).
 
Listings of individual subject laboratory results will be provided. Laboratory results, Clinically Significant and change from baseline for selected lab tests will be summarized by treatment at scheduled visits.
 
Twelve-lead ECGs and vital signs measurements will be listed by subject and summarized by incidence of events/abnormalities or descriptive statistics as appropriate. Individual data for physical examination findings, prior and concomitant medications and medical history will be provided.

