2. STUDY OBJECTIVE AND ENDPOINTS

2.1 Objectives:

2.1.1 Primary Efficacy Objective:

Assess the efficacy of VGT-309 with near-infrared (NIR) imaging for lesion visualization when compared to standard surgical techniques in subjects undergoing surgery for proven or suspected cancer in the lung.

2.1.2 Secondary Efficacy Objective:

Assess the utility of VGT-309 with NIR imaging to identify cancerous tissue as confirmed by histopathology.

2.1.3 Safety Objective:

Determine the safety and tolerability of VGT-309 in subjects with proven or suspected cancer in the lung.

2.2 Endpoints:

2.2.1 Primary Efficacy Endpoint:

Identify the proportion of subjects with at least one Clinically Significant Event (CSE) as defined by:

- A. Intraoperative localization of one or more preoperatively identified lung lesions using VGT-309 with NIR imaging when standard surgical techniques using white light and/or palpation failed to identify the lesion(s), and lesion(s) are confirmed by histologic examination to be other than normal lung tissue.
- B. Identification of one or more synchronous or occult lung lesions using VGT-309 with NIR imaging when standard surgical techniques using white light and/or palpation and preoperative imaging failed to identify the lesion(s), and lesion(s) are confirmed by histologic examination to be cancerous or precancerous.
- C. Identification of fluorescence within ≤ 10 mm from the inside edge of the closest staple line as measured by the investigator *ex vivo* in the operating room using NIR imaging, with pathologic margin confirmed by histologic examination to be ≤ 10 mm.
NOTE: Margins from excisions of known or suspected metastases at the time of the surgery, OR diagnostic wedge resections where a completion lobectomy or segmentectomy was subsequently performed, will not be considered for Margin CSE inclusion.
- D. Identification of lymph nodes by VGT-309 with NIR imaging confirmed by histologic examination to be cancerous.

2.2.2 Secondary Efficacy Endpoints:

To evaluate the sensitivity, positive predictive value (PPV), and 1-PPV of VGT-309 with NIR imaging for lesion(s) *in vivo*:

- 1. Sensitivity is defined as the probability that the tissue fluoresces when it is cancer, as confirmed by histology $(TP/(TP+FN))$ *
- 2. Positive predictive value (PPV) is defined as the probability that a tissue sample contains cancer on histologic exam if it fluoresces $((TP/(TP+FP))$ *

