8.3 Intra-operative Evaluations

During the surgery, the Surgeon/Investigator will first utilize standard surgical techniques using white light and/or palpation followed by *in situ* NIR fluorescence imaging using an NIR imaging system capable of detecting ICG for localization of the primary tumor and any potential synchronous or occult lesions and lymph nodes.

The number and location of pulmonary nodules and synchronous lesions that are visualized by standard techniques and/or by VGT-309 NIR fluorescence imaging will be recorded. Lymph nodes visualized by VGT-309 NIR fluorescence imaging will be identified and recorded by nodal station and zone.

Following extraction of any tumor/nodules, synchronous lesions, and lymph nodes, *ex vivo* NIR fluorescence imaging will take place in the operative suite prior to closing the surgical field.

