10.3.2 Primary Hypothesis

The primary study hypothesis is that VGT-309 with NIR imaging is superior to white light and/or palpation for the intraoperative localization of preoperatively identified lung lesions.

The null hypothesis for the primary endpoint is that $\leq 10\%$ of subjects will have at least one CSE, while the alternative hypothesis is that proportion of subjects with at least one CSE will exceeds 10% as demonstrated by at least 15/86 (17.4%) evaluable subjects with at least one CSE.

For the primary endpoint analysis, the proportion of subjects with at least 1 CSE will be tested under the null hypothesis that this proportion is $\leq 10\%$.

$$H_0: p \leq 10\%$$

The alternative hypothesis states that the proportion of evaluable subjects with at least 1 CSE will be greater than 10%:

$$H_a: p > 10\%$$

The primary analysis will use the EP population. This analysis may be repeated using the ITT population. One-sided 2.5% exact binomial test will be used to test the null hypothesis. Clopper-Pearson exact two-sided 95% confidence intervals will be reported.

For the secondary endpoint analysis sensitivity, PPV, and 1-PPV will be calculated and presented along with 95% confidence intervals using GEE model analysis to factor in within-subject correlation for subjects with multiple tumors.

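### Margin and lymph-node CSEs need no failure of standard technique, so rejecting the 10% null does not by itself show superiority to white light or palpation

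*Protocol*

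**What the plan says.** Protocol 2.1.1 sets the primary objective as efficacy "for lesion visualization when compared to standard surgical techniques". Protocol 10.3.2 and SAP 9.2 word the primary hypothesis more narrowly: superiority to white light and palpation (the Protocol has and/or) for finding, during surgery, lesions identified beforehand.

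The endpoint is the proportion of subjects with at least one CSE. The four types are defined alike in the Protocol synopsis, Protocol 2.2.1, SAP 3.1 and SAP 9.1 (the SAP numbers them 1 to 4):

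- **A**, known lesion: NIR localizes it after white light and/or palpation failed.
- **B**, synchronous or occult lesion: NIR finds it after standard technique and preoperative imaging both failed.
- **C**, margin: "Identification of fluorescence within ≤ 10 mm from the inside edge of the closest staple line", measured ex vivo, with a pathologic margin of 10 mm or less.
- **D**, node: "Identification of lymph nodes by VGT-309 with NIR imaging confirmed by histologic examination to be cancerous".

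The synopsis and Protocol 10.3.2 set success at 15 or more of 86 evaluable subjects. Protocol 10.3.1 says that the test is not a treatment comparison. SAP 9.3 adds a descriptive summary of CSE frequency by type. Protocol 8.3 records nodules and synchronous lesions seen by standard technique and/or NIR, but for nodes it says only: "Lymph nodes visualized by VGT-309 NIR fluorescence imaging will be identified and recorded by nodal station and zone".

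**The concern.** Types A and B carry the comparison in their definitions: the subject counts only because standard technique missed something. Types C and D have no such condition. A node already suspicious on imaging and removed as routine counts if it fluoresces and is positive. A close margin already apparent to the surgeon counts if fluorescence lies within 10 mm and pathology agrees. Nor is either one localization of a preoperatively identified lung lesion, which is what the worded hypothesis is about.

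Because one event of any type is enough, the pooled proportion mixes what NIR adds with how often nodal disease and close margins occur and fluoresce. At stake is the conclusion that may be drawn. The trial could meet its primary endpoint and report superiority to white light and palpation when few or none of the counted events were missed by those methods.

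**Working it through.** **Inputs.** The synopsis gives the planning basis as "assuming a 20% true rate of at least one CSE, two-sided 5% Type 1 error and 80% power", a null rate of 10%, and a design that "requires 86 evaluable subjects in the primary analysis group". Protocol 10.3.2 names the test: "One-sided 2.5% exact binomial test will be used to test the null hypothesis". The success rule is 15/86. No document gives a rate for any single CSE type, so every such rate below is an assumption.

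**The plan's own figures.**

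- Sample size, normal approximation: n = [(1.960·√(0.10·0.90) + 0.842·√(0.20·0.80)) / (0.20 − 0.10)]² = 85.5, rounded up to 86. This reproduces.
- Cut-off: P(X ≥ 15 | n = 86, p = 0.10) = 0.0230, and P(X ≥ 14) = 0.0461. So 15 is the right cut-off at one-sided 2.5%.
- Clopper-Pearson interval at 15/86, from the 2.5% quantile of Beta(15, 72) and the 97.5% quantile of Beta(16, 71): 10.1% to 27.1%. This reproduces.

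**No A or B events.** Let q be the true proportion of subjects with a C or D event. The chance of meeting the rule is P(X ≥ 15 | n = 86, p = q):

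| Assumed C/D rate q | Chance of at least 15/86 |
|---|---|
| 8% | 0.3% |
| 10% | 2.3% |
| 12.5% | 11.4% |
| 15% | 30.5% |
| 17.5% | 55.0% |
| 20% | 76.3% |

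In every row the count of A and B events is zero.

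**A small gain.** Assume A/B events in 5% of subjects and C/D events in 15%, independently. The composite rate is 1 − 0.95 × 0.85 = 19.25%, and the chance of meeting the rule is 70.6%. On A and B events alone, at 5%, it is about 0.002%.

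**What an A/B-only estimate would look like at n = 86.** As an illustration, 5/86 is 5.8%. Its Clopper-Pearson interval, from Beta(5, 82) and Beta(6, 81), is 1.9% to 13.0%. The ratio of upper to lower limit is 13.0/1.9 ≈ 6.8, against 27.1/10.1 ≈ 2.7 at 15/86. Such an analysis can describe the A/B rate but is not powered for a test against 10%.

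**Can D events be split afterwards?** Protocol 8.1 and 8.3 have the surgeon use standard technique before NIR for nodes as well as lesions. The endpoint makes no use of that result for nodes, and 8.3 names only NIR-visualized nodes for recording. For A and B the needed record is specified.

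**The case against.** The strongest reply is that this is a defensible composite for a single-arm Phase 2 study. Histologically confirmed nodal disease and close margins matter clinically, Protocol 10.3.1 disclaims a treatment comparison, and the summary by type in SAP 9.3 would show if C and D carried the result. Much of this stands, and it is why the composite can stay. But a descriptive table changes neither the success rule nor the worded hypothesis, and it does not separate D events that standard technique missed from those it did not. Section 10.3.1 sharpens the conflict: if the test is not a comparison, its rejection cannot establish superiority.

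A reader might infer four stronger things that the documents do not support.

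- *That type I error is inflated.* It is not. At a composite rate of 15% or 20% the null of 10% or less is false, and rejecting it is correct for the hypothesis tested.
- *That success without any gain is likely.* That depends wholly on the C/D rate, which is not given. At 8% the chance is 0.3%.
- *That the incremental part of D is lost for good.* The eCRF is not among the documents, and SAP 9.3 tabulates CSEs against pre-operative and post-operative stage, which gives an indirect signal. One can say only that no visible text guarantees the split.
- *That 10% is a meaningless benchmark.* Protocol 10.1 shows no text and SAP section 5 is redacted, so a rationale may exist there.

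The Note under type C excludes some metastasis and diagnostic-wedge margins. It narrows C but adds no comparator.

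**Conclusion.** The point holds as one of interpretation. Rejecting a composite rate of 10% or less shows that more than 10% of subjects had some CSE. It does not by itself show that NIR is superior to white light and palpation for localizing known lesions, because C and D events count with no failure of standard technique and can meet 15/86 on their own. The definitional part rests on fully visible text and needs no assumption. The size rests on an assumed C/D rate: negligible at 8%, material above 10%, and 30.5% to 76.3% between 15% and 20% when there are no A or B events. This should be fixed before the SAP is final. It does not invalidate the composite endpoint.

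**What to change.** 1. Keep the composite. Reword the primary hypothesis in Protocol 10.3.2 and SAP 9.2 to what is tested: the proportion of subjects with any CSE exceeds 10%.
2. In SAP 9.3, pre-specify a key supportive analysis: the proportion of subjects with at least one type A or B event, with a Clopper-Pearson 95% interval, in the Evaluable and ITT populations. Limit any claim of benefit over standard technique to this analysis. Protocol 8.3 already calls for the data.
3. Add an eCRF item, completed before in situ NIR, stating whether each node was suspicious on preoperative imaging or by white light or palpation. Add to the supportive analysis the D events in nodes not so identified.
4. Report type C separately, as an event without a comparator. A surgeon's margin estimate made before any NIR is not workable: in situ NIR precedes extraction, the margin is measured on the specimen, and the visible text describes no standard-technique margin measurement.

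The cost is wording in two documents, one added analysis and one data item. The supportive analysis will show a lower rate with a relatively wider interval, and 86 subjects were not sized for it, so present it as estimation rather than a powered test against 10%. Adding a comparator condition to C and D within the primary endpoint itself is a larger trade-off and is not needed to resolve the point.

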3. STUDY DESIGN

This is a Phase 2, multi-center, open-label study to evaluate the safety and efficacy of VGT-309, a tumor-targeted, activatable fluorescent imaging agent, in subjects undergoing surgery for proven or suspected cancer in the lung.

Following agreement with and signing of the informed consent, subjects will undergo screening measurements for the study within 4 weeks prior to the anticipated dosing:

1. Medical, surgical and medication history.
2. Complete physical exam, including vital signs and height
3. Weight (needed for dose calculation)
4. Chemistry, hematology, coagulation and urinalysis with microscopy clinical laboratory studies.
5. 12-lead ECG.
6. Serum pregnancy test for females of child-bearing potential.

After meeting all enrollment criteria, each subject will receive 0.32 mg/kg VGT-309 by IV administration 12-36 hours prior to surgery (refer to section VGT-309 Dosing, below). Subjects will be observed for 1 hour after dosing is completed and asked about possible treatment emergent adverse events.

Subjects will undergo surgical resection within 12-36 hours after completion of VGT-309 dosing. Measurements of efficacy will be taken during surgery and during the pathological examination of all surgical specimens. (Refer to Efficacy Endpoints and Efficacy Assessments sections).

Following surgery, subjects will be monitored for safety during their hospitalization. Between 7 to 14 and 25 to 35 days after surgery, the subjects will return to the clinic or have a telehealth visit for final safety assessments. At the last visit, if there are no adverse events requiring further follow up, subjects will then be released from the study.

If a subject chooses to withdraw from the study prior to the final visit, they will be asked to undergo a final safety assessment before their departure.

4. STUDY DRUG – VGT-309

VGT-309 will be administered over 15 to 20 minutes as an IV infusion. Following are details related to VGT-309 preparation, packaging and labeling and storage. Additional details will be supplied in the Pharmacy Manual.

4.1 VGT-309 Description

VGT-309 will be supplied in a lyophilized form in 5ml vials containing 10mg of VGT-309.

4.2 VGT-309 Proposed Dose

The dose for this study is 0.32mg/kg of VGT-309

4.3 VGT-309 Preparation

VGT-309 is stored frozen and must be thawed at room temperature for at least 30 minutes but not more than 2 hours before it is prepared for dosing.

4.4 VGT-309 Dose Administration

VGT-309 will be given between 12-36 hours prior to prior to induction of general anesthesia for the planned surgery as an IV infusion by syringe pump over 15 to 20 minutes.

4.5 VGT-309 Storage and Accountability

VGT-309 will be stored frozen ($-20^{\circ}\text{C} \pm 10^{\circ}\text{C}$) in a secure, locked area under the responsibility of the clinical research unit pharmacy or its designee.

The Investigator or Investigational Pharmacy must maintain accurate records of the receipt of all study drug, including date received, lot number, amount received, condition of the package and the disposition. Dispensing records will be maintained including the date and amount of study drug dispensed and the identity of the subject receiving the study drug.

Empty and partially used vials can be destroyed per the study site Study Drug Destruction SOPs upon completion of VGT-309 dispensing.

Following final reconciliation, unused study drug should be returned to Vergent Bioscience, Inc., or its designee.

4.6 VGT-309 Packaging and Labeling

Labels will be in compliance with all applicable regulatory requirements for the labeling of active pharmaceutical ingredients for the US and Australia as noted below:

- For the US – according to 21 CFR § 312.6 labels will contain:

- “Limited by Federal Law to Investigational Use” statement
 - IMP name, route of administration and amount of VGT-309 in the vial.
 - Lot number.
 - Storage conditions.
 - Sponsor name (Vergent Bioscience, Inc).
 - Manufacturer.
- For Australia - according to Annex 13 of GMP labels will contain:
 - “For Clinical Trial Use Only: Per Protocol” statement
 - IMP name, route of administration and amount of VGT-309 in the vial
 - Protocol number
 - Retest date and batch number
 - Storage conditions
 - Sponsor name (Vergent Bioscience Australia Pty LTD)

5. SUBJECT POPULATION

5.1 Enrollment

Approximately 100 subjects scheduled to undergo standard of care surgical resection for a lung nodule that is already proven or suspected to be cancer in the lung will be enrolled to ensure at least 86 evaluable subjects.

5.2 Inclusion Criteria

In order to be enrolled in the study, the subject must:

1. Be willing and able to sign the informed consent and comply with study procedures.
2. Be at least 18 years of age.
3. Meet the following conditions:
 - a. Female participants must be of non-childbearing potential, or,
 - b. If of childbearing potential be non-pregnant or non-lactating and agree to use highly effective contraception from screening through Day 30 after treatment.
 - c. Male participants, if not surgically sterilized, and if engaging in sexual intercourse with a female partner of childbearing potential, must be willing to use highly effective contraception from screening through 30 days post-dose and agree not to donate semen during this waiting period.
 - d. Highly effective contraception involves the use of a condom for the male, plus one of the following for the female:
 - Oral, injectable, implantable, intravaginal, or transdermal hormonal contraceptives, or
 - Intrauterine device or intrauterine hormone-releasing system.

NOTE: Subjects who abstain from heterosexual intercourse as their usual and preferred lifestyle, will not be required to use contraception as described above. They are required to maintain abstinence from screening through Day 30.

NOTE: Subjects in a same sex relationship, must use a barrier form of contraception (e.g., condom, diaphragm) to protect against the transfer of the study drug in any bodily fluids.

4. Have a lung nodule or mass that might be considered primary lung cancer or lung metastases, whether or not it is biopsy-proven prior to surgery.
5. Be scheduled to undergo standard of care surgical resection for a lung nodule or mass with diagnostic and/or curative intent.
6. Have acceptable kidney and liver functions at study entry as evidenced by:
 - a. $ALT/AST \leq 1.5$ times the upper limit of normal,
 - b. Calculated Creatinine Clearance ($CrCl$) ≥ 50 ml/min (manual calculation using Cockcroft-Gault equation),
 - c. Total bilirubin ≤ 1.5 times the upper limit of normal.
7. Have an ECOG score of 0-2.
8. Meet all standard surgical and general anesthesia requirements.
9. Have not participated in an interventional clinical trial within the last 30 days (participation in a disease registry or quality of life study is not exclusionary).

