Inclusion Criteria	
In order to be enrolled in the study the subject must:
 
 Be willing and able to sign the informed consent and comply with study procedures. Be at least 18 years of age.

	
3. Meet the following conditions:
 
 Female participants must be of non-childbearing potential, or, If of childbearing potential, be non-pregnant or non-lactating and agree to use highly effective contraception from screening through Day 30 after treatment. Male participants, if not surgically sterilized, and if engaging in sexual intercourse with a female partner of childbearing potential, must be willing to use highly effective contraception from screening through 30 days after treatment and agree not to donate semen during this waiting period. Highly effective contraception involves the use of a condom for the male, plus one of the following for the female: 
 Oral, injectable, implantable, intravaginal, or transdermal hormonal contraceptives, or Intrauterine device or intrauterine hormone-releasing system NOTE: Subjects who abstain from heterosexual intercourse as their usual and preferred lifestyle, will not be required to use contraception as described above. They are required to maintain abstinence from screening through Day 30 after treatment. Note: Subjects in a same sex relationship, must use a barrier form of contraception (e.g., condom, diaphragm) to protect against the transfer of the study drug in any bodily fluids. 
4. Have a lung nodule or mass that might be considered primary lung cancer or lung metastases whether or not it is biopsy-proven before surgery.
 
5. Be scheduled to undergo standard of care surgical resection for a lung nodule or mass with diagnostic and/or curative intent
 
6. Have acceptable kidney and liver functions at study entry as evidenced by:
 
 $ALT/AST \leq 1.5$ times the upper limit of normal Calculated Creatinine Clearance (CrCl) ≥ 50 ml/min (manual calculation using Cockcroft-Gault equation) Total bilirubin ≤ 1.5 times the upper limit of normal 
7. Have an ECOG score of 0-2.
 
8. Meet all standard of care surgical and general anesthesia requirements.
 
9. Have not participated in an interventional clinical trial within the last 30 days (participation in a disease registry or quality of life study is not exclusionary).

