5.3 Exclusion Criteria

Subjects may not be enrolled in the study if:

1. They are not a candidate for standard of care surgery based on opinion of the surgeon, anesthesiologist, or other consulting physician.
2. They have a known allergy or reaction to ICG, other radiographic contrast agent, or any component of VGT-309.
3. They have congenital long QT syndrome or $QTcF > 470$ ms by history or at Screening ECG.
4. They have received chemotherapy or immunotherapy within 4 weeks prior to study enrollment.
5. They are prisoners, institutionalized individuals, or are unable to consent for themselves.
6. They have any other co-morbidity or habit that the Investigator believes will interfere with their ability to comply with and complete the study.

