6.1.2 Screening (Days -30 to -1)

With 30 days of obtaining the informed consent, the following assessments will be done to establish a subject's eligibility for the study. Note: in cases where subjects have given consent for general pre-screening at the site, some of these assessments may be done by chart review.

When possible, the assessments should be done in the order listed here to avoid the demands of sample collection and ECG prior to the subject passing basic entry criteria requirements.

1. Review of eligibility requirements – inclusion and exclusion criteria.
2. Collection of demographic information and medical and surgical history, including review of prior and ongoing medications taken in the previous 30 days. Note: Specific attention should be paid to collecting information on any prior cancer and the treatment received for it, regardless of when that treatment was given.
3. Physical Exam.
4. Height and weight measurements (BMI will be calculated in the EDC).
5. Vital signs measurement (blood pressure, pulse rate, respiratory rate and oral/tympanic temperature).
6. Standard 12-lead ECG taken in triplicate (subject should be resting in a supine position for at least 5 minutes prior to the first ECG. There is no pausing between each of the 3 ECGs to be taken). (QTcF will be calculated as the ECG results are entered in the EDC.)
7. Blood sample collection for clinical chemistry, hematology and coagulation.
8. Urine sample collection for urinalysis, including microscopy.
9. In women of child-bearing potential, blood sample for serum pregnancy test.

Upon establishment of eligibility, subjects are scheduled for their VGT-309 infusion to take place 12-36 hours prior to induction of general anesthesia for their scheduled surgery.

NOTE: Screening exams may be done on Day 1 (Day of VGT-309 dosing) provided all results are available and the subject qualifies for the study prior to dosing.

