6.1.3 Day 1: VGT-309 Dosing

Subjects will check in to the hospital or infusion center as scheduled. After confirming their eligibility by reviewing their medical and surgical history and concomitant medications for any changes since screening, those subjects still considered eligible will undergo the following:

1. Targeted Physical Exam (Focus on heart, lungs and any area of change since screening).
Note: changes from Screening to be recorded in Medical History section of the CRF.
2. Measurement of weight for dose calculation unless taken within the prior 7 days or if site SOPs require that the subject's weight be taken before the dose is prepared on the day of dosing).
3. Vital signs measurement (blood pressure, pulse rate, respiratory rate and oral/tympanic temperature).
4. In women of child-bearing potential, urine or serum sample for pregnancy test.
5. Blood sample for chemistry, hematology, coagulation. (**ONLY** if not done within 4 weeks prior to dosing).
6. Urine sample collection for urinalysis with microscopy (**ONLY** if not done within 4 weeks prior to admission).
7. Standard 12-lead ECG in triplicate within 10 MINUTES PRIOR to start of dosing (subject should be resting in a supine position for at least 5 minutes prior to the first ECG. There is no pausing between each of the 3 ECGs).
8. VGT-309 dosing to take place at 12-36 hours prior to induction of general anesthesia. (Refer to Section 4: Study Drug – VGT-309, for instructions on dose preparation and dosing procedures).
9. Assessment for potential adverse events begins with the start of dosing. (See Section 9.2.1.2)
10. Upon completion of dosing, VGT-309 subjects:
 - will be observed for 1 hour and queried for possible adverse events,
 - will have ECGs taken in triplicate, between 1 to 10 minutes and 30 +/- 5
 - will have vital signs taken at 30 +/- 5 minutes and 60 minutes +/- 5 minutes.

NOTE: Subjects may be allowed to leave the hospital grounds/infusion center and return prior to surgery, provided they have been observed for at least 1 hour following their dose of VGT-309 and the Investigator does not observe any concerning safety issues

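### Inclusion 3b joins its pregnancy and lactation conditions with *or*, so on its literal wording a woman with only one of the two conditions meets that limb; the connector should be corrected

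*Protocol*

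**What the plan says.** Protocol section 5.2, item 3b, reads: "If of childbearing potential be non-pregnant or non-lactating and agree to use highly effective contraception from screening through Day 30 after treatment". The inclusion criteria in the synopsis use the same connector: "be non-pregnant or non-lactating and agree to use highly effective contraception". Neither place corrects the other.

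A note under item 3 offers another way to meet the contraception part: "Subjects who abstain from heterosexual intercourse as their usual and preferred lifestyle, will not be required to use contraception as described above". Such subjects must stay abstinent through Day 30.

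Section 5.3 lists six exclusions, and none names pregnancy or lactation. The most general is discretionary: "They have any other co-morbidity or habit that the Investigator believes will interfere with their ability to comply with and complete the study".

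Pregnancy is tested twice. Section 6.1.2 introduces the screening list by saying that "the following assessments will be done to establish a subject's eligibility for the study", and its last item is "In women of child-bearing potential, blood sample for serum pregnancy test". Section 6.1.3 adds a Day 1 item: "In women of child-bearing potential, urine or serum sample for pregnancy test". Section 9.2.4 covers the reporting of pregnancies that arise after dosing.

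**The concern.** Item 3b uses *and* for a requirement that is plainly cumulative, the contraception agreement. It uses *or* between two conditions that appear to be meant cumulatively as well. Taken at its word, the criterion asks a woman to be free of one condition, not of both.

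Enrolment is checked against the written criteria. On the literal text, a site that enrols a breastfeeding woman who is not pregnant, and who meets the contraception or abstinence limb, has not departed from 3b. The requirement in section 10.2 that Evaluable Population subjects were eligible would not pick her up on this ground either. Up to seven centers in two countries would have to infer the rule from its context.

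What is at stake is the clarity of a safety-related entry criterion. The primary endpoint, the sample size and the planned tests are not touched.

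**Working it through.** The plan gives no figure on this point, so there is nothing to reproduce. The check is a truth table, followed by a reading of each readable place that could close the gap.

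**Truth table.** Let P = pregnant, L = lactating, and C = the contraception or abstinence limb is met. As written, 3b = [(not P) or (not L)] and C. With the connector changed, 3b = [(not P) and (not L)] and C. If C fails, all four combinations fail under either wording. If C holds:

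| P | L | with *or* (as written) | with *and* |
|---|---|---|---|
| no | no | meets | meets |
| no | yes | meets | fails |
| yes | no | meets | fails |
| yes | yes | fails | fails |

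So *or* passes 3 of 4 combinations and *and* passes 1 of 4. These are counts of logical cases, not of subjects.

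**Does limb C remove the two extra cases?** A breastfeeding woman can agree to the listed methods, so C does not keep her out. For a pregnant woman, agreeing to a condom plus a hormonal method or an intrauterine device is hard to reconcile with an ongoing pregnancy. She would more plausibly come in through the abstinence note. C narrows the pregnancy case without closing it.

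**Do the exclusions remove them?** None of the six names either condition.

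**Does screening remove them?** The serum test is among the assessments done to establish eligibility, and section 6.1.2 schedules the infusion only once eligibility is established. The purpose is evident. However, no readable sentence states the effect of a positive result, and the criterion against which eligibility is judged is 3b itself. The list has no lactation item.

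**Does Day 1 remove them?** Section 6.1.3 confirms eligibility from changes in history and concomitant medications, and then gives a list for those still eligible. The pregnancy test is item 4 and dosing is item 8. The order points to intent, but no sentence links the result to eligibility. The note closing section 6.1.2 requires results to be available, and the subject to qualify, before dosing. It is worded for screening exams done on Day 1 and does not expressly cover the separate Day 1 test. Lactation is again not mentioned.

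**Result.** For pregnancy, the surrounding procedures show what was meant and partly mitigate the wording. For lactation, no readable text outside 3b addresses it.

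**The case against.** The strongest reply is that this is a one-word slip whose meaning nobody would mistake. Women are tested for pregnancy at screening, for the stated purpose of establishing eligibility, and again before dosing on Day 1. They must commit to contraception or abstinence. Inclusion 8 and exclusion 1 bring in surgical and anesthesia judgment. An investigator would be expected to act on a positive test. Most of this stands for pregnancy, and it is why the point is a correction of wording and not a claim that pregnant women would be dosed. It does not answer the lactation half.

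A reader might go further in four ways that the documents do not support:

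- **That 3b is the only protection against exposure in pregnancy.** The two tests and the contraception or abstinence commitment are further layers, even though none states a bar in words.
- **That the Day 1 result need not be known before the infusion.** Section 6.1.3 does not say this. It is silent, and it lists the test ahead of dosing.
- **That section 9.2.4 contradicts 3b.** That section concerns pregnancies arising between dosing and the end of the study. It is evidence of intent and does not address pregnancy at entry.
- **That three combinations in four measures the risk in this trial.** The table leaves frequency out altogether. The documents give no expected number of such women, and no readable figure on reproductive harm.

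It is also fair to say that sections 6 and 6.1 defer to Attachment A, the Schedule of Assessments. Attachment A cannot be read in the available text, and parts of the synopsis are blacked out. A rule on pregnancy or lactation may stand there. It would reduce the practical gap, but 3b would still carry the wrong connector in two places.

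**Conclusion.** The concern holds as a defect in the wording of an operative eligibility criterion. In section 5.2 and in the synopsis, 3b literally accepts a woman who has one of the two conditions, provided she meets the contraception or abstinence limb. That does not fit the protocol's own pregnancy testing and contraception requirement. The gap is partly mitigated for pregnancy; for lactation, nothing readable outside 3b fills it.

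The practical size is likely to be small. Few subjects in a lung-surgery population should be affected, but that is a judgment, since the documents give no number. No endpoint, sample size or analysis changes. The conclusion rests on the literal reading of *or*, on the inference from the tests and the contraception rule that both conditions were meant to hold, and on the readable text alone.

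**What to change.** In section 5.2, item 3b, and in the synopsis, correct the connector so that both listed conditions must hold, for example *non-pregnant and non-lactating*.

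Then reconcile 3b with sections 6.1.2 and 6.1.3, so that the protocol says how the Day 1 pregnancy test result bears on eligibility. Check Attachment A for consistency at the same time. What the rule should be is a clinical decision for the sponsor, and none is proposed here.

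The cost is one word in two places, plus whatever short text the reconciliation needs, in a protocol amendment. The wording correction adds no test or visit and leaves the SAP unchanged.
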